2.6.1.3 Handling of missing values/censoring/discontinuations for PFS, LFS and EFS

For participants without PFS/EFS/LFS events, PFS/LFS/EFS are censored at the last adequate assessment (response assessment for PFS/EFS, bone marrow/hematology assessment for LFS).

This is the last response/bone marrow/hematology assessment conducted that is not considered as unknown.

An event occurring after two or more consecutive missing response assessments (not done or unknown) is censored in the analysis at the last adequate response assessment before the event date and reason for censoring then summarized as 'Event documented after two or more missing response assessments'.

An exact rule to determine whether there are two missing assessments is therefore needed. This rule will be based on the distance between the last adequate response assessment date and the event date. If the distance is larger than threshold D_2 then the analysis will assume that there are two missing assessments. This threshold D_2 is defined as two times the protocol specified interval between the response assessments plus the allowed window around the assessments. The protocol defines that response assessment has to be done at least at the time of bone marrow assessments that are to be done:

- Pre-dose on C3D1, then
- From C7D1, bone marrow assessments will be performed every 3 cycles (12 weeks) until C13D1 (C7D1, C10D1, C13D1), then
- Every 6 cycles (24 weeks) until C25D1 (C19D1 and C25D1) and thereafter every 12 cycles (48 week, visit: C37D1, C49D1 etc.) and as clinically indicated during the treatment period).
- At least every 12 months during follow-up for efficacy

As per the protocol, a window of +/-1 week from the planned visit date is allowed for BMA procedures. During the post-treatment and survival follow-up phases, a visit window of +/-2 weeks is allowed.

The censoring reason will be summarized as:

- 1. Ongoing without event
- 2. New anti-cancer therapy
- 3. Withdrew consent
- 4. Lost to follow-up
- 5. Event documented after two or more missing response assessments
- 6. Discontinuation due to participant/physician/guardian's decision

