The efficacy follow-up period will last until participant's documented disease progression (per IWG criteria Table 8-2), death, lost to follow-up, or withdrawal of consent, or the end of the study whichever comes first. Post-treatment antineoplastic therapies, including HSCT, will continue to be captured during survival follow-up (see Section 9.1.1.3 and Table 8-1).

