Progression free survival (PFS)

PFS is defined as the time from start date of treatment to date of relapse, progression (including transformation to acute leukemia per WHO 2016 classification) or death due to any cause. If a participant is not known to have relapsed progressed nor died, PFS will be censored at the last adequate response assessment (on or before the cut-off date). Progression/relapse or death after HSCT, interruptions, or discontinuation of study treatment due to any reason will be taken into account. However, Progression/Relapse, death occurring after initiation of new antineoplastic therapy will not be considered as event and PFS will be censored at last adequate response assessment.

In case of two or more missing assessments prior to documented progression, relapse or death, PFS will be censored at the last adequate response assessment prior to the documentation of progression, relapse or death.

PFS will be estimated using the Kaplan-Meier method. The median PFS along with 95% confidence interval will be presented.

Leukemia free survival (LFS)

LFS is defined as the time from start of treatment to transformation to acute leukemia as per investigator assessment defined as the following:

- $\geq 20\%$ blasts in bone marrow/ peripheral blood (per WHO 2016 classification)
- Diagnosis of extramedullary acute leukemia
- Death due to any cause

whichever occurs first.

If a participant is known to not have progressed to leukemia, then LFS will be censored at the last bone marrow/peripheral blood assessments (on or before the cut-off date). All of three events ($\geq 20\%$ blasts in bone marrow/peripheral blood, diagnosis of extramedullary acute leukemia or death) after HSCT, interruptions, or discontinuation of study treatment due to any reason will be taken into account. However, events occurring after initiation of new antineoplastic therapy will not be considered as event and LFS will be censored at last assessment of bone marrow/peripheral blood, diagnosis of extramedullary acute leukemia or survival follow-up prior to initiation of new antineoplastic therapy.

LFS will be estimated using the Kaplan-Meier method. The median LFS along with 95% confidence interval will be presented.

Overall Survival (OS)

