Participants treated with sabatolimab at 800 mg Q4W who failed to achieve CR within 6 cycles of treatment will have their EFS event documented at start of treatment. If participant discontinued treatment due to any reason (including death) prior to 6 cycles and without CR will be considered as EFS event documented at start of treatment date.

Progression/Relapse, or death events after HSCT, and transfusion of blood products, will be taken into account. However, Progression/Relapse, or death, occurring after initiation of new antineoplastic therapy, will not be considered an event and EFS will be censored at the last adequate response assessment prior to the new antineoplastics therapy.

In case of two or more missing assessments prior to documented progression, relapse or death, EFS will be censored at the last adequate response assessment prior to the documentation of relapse or death.

EFS will be estimated using the Kaplan-Meier method. The median EFS along with 95% confidence interval will be presented.

Progression free survival (PFS)

PFS is defined as the time from start date of treatment to date of relapse, progression (including transformation to acute leukemia per WHO 2016 classification) or death due to any cause. If a participant is not known to have relapsed, progressed nor died, then PFS will be censored at the last adequate response assessment (on or before the cut-off date). Progression/relapse or death occurring after a). HSCT, b). interruptions or c). discontinuation of study treatment due to any reason will be taken into account. However, Progression/Relapse, death occurring after initiation of new antineoplastic therapy will not be considered an event and PFS will be censored at the last adequate response assessment.

In case of two or more missing assessments prior to documented progression, relapse or death, PFS will be censored at the last adequate response assessment prior to the documentation of progression, relapse or death.

PFS will be estimated using the Kaplan-Meier method. The median PFS along with 95% confidence interval will be presented.

Leukemia Free survival (LFS)

LFS is defined as the time from start of treatment to transformation to acute leukemia as per investigator assessment defined as the following:

- \geq 20% blasts in bone marrow/ peripheral blood (per WHO 2016 classification)
- Diagnosis of extramedullary acute leukemia
- Death due to any cause

whichever occurs first.

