If a participant is known to not have progressed to leukemia as defined by the criteria mentioned above, then LFS will be censored at the last bone marrow/peripheral blood assessments (on or before the cut-off date). Any of the three events (i.e. $\geq 20\%$ blasts in bone marrow/peripheral blood, diagnosis of extramedullary acute leukemia or death) occurring after HSCT, interruptions, or discontinuation of study treatment due to any reason will be taken into account. However, events occurring after initiation of new antineoplastic therapy will not be considered

an event and LFS will be censored at the last adequate assessment of bone marrow and/or peripheral blood, or diagnosis of extramedullary acute leukemia prior to initiation of new antineoplastic therapy.

In case of two or more missing assessments prior to documented progression to leukemia, LFS will be censored at the last adequate assessment (bone marrow and/or hematology assessment) prior to the documentation of progression to leukemia.

LFS will be estimated using the Kaplan-Meier method. The median LFS along with 95% confidence interval will be presented.

Overall Survival (OS)

OS is defined as the time from start date of treatment to date of death due to any cause. If a participant is not known to have died, then OS will be censored at the latest date the participant was known to be alive (on or before the cut-off date). All deaths will be taken into account whenever the death occurred, i.e. even after new anti-neoplastic therapy, HSCT, interruptions, or discontinuation of study treatment due to any reason.

The OS censoring reason will be summarized as 'Alive' or 'Lost to follow-up'. Participants not known to have died will have the censoring reason 'Lost to follow-up' if the reason for discontinuation from study is 'Lost to follow-up' or 'Withdrawal of consent'. Otherwise, participants will have the censoring reason 'Alive'.

OS will be estimated using the Kaplan-Meier method. The median OS along with 95% confidence interval will be presented.

Improvement of RBC/platelets transfusion independence

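### SAP 2.6.1.3 and 2.6.1.2 conflict on whether the two-missing-assessments rule censors deaths in leukemia-free survival (LFS)

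*SAP*

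**What the plan says.** Three places govern LFS censoring.

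- **SAP 2.6.1.3** is headed "Handling of missing values/censoring/discontinuations for PFS, LFS and EFS". Its rule is: "An event occurring after two or more consecutive missing response assessments (not done or unknown) is censored in the analysis". It makes the test mechanical. If the distance from the last adequate response assessment to the event exceeds D_2, two assessments are taken to be missing. D_2 is twice the scheduled interval plus the visit window.
- **SAP 2.6.1.2** gives LFS its own, narrower rule: "In case of two or more missing assessments prior to documented progression to leukemia, LFS will be censored at the last adequate assessment". Death is not named. The parallel EFS and PFS rules in the same section do name it: "In case of two or more missing assessments prior to documented progression, relapse or death". For LFS the section also counts "diagnosis of extramedullary acute leukemia or death) occurring after HSCT, interruptions, or discontinuation of study treatment due to any reason".
- **Protocol 12.5.1.2** counts "diagnosis of extramedullary acute leukemia or death) after HSCT, interruptions, or discontinuation of study treatment due to any reason will be taken into account". It has a missing-assessment rule for EFS and PFS but none for LFS, and SAP section 3 does not list one as a change.

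Both documents make one exception for LFS events, including deaths. In the protocol's words: "However, events occurring after initiation of new antineoplastic therapy will not be considered as event and LFS will be censored".

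On follow-up, protocol 8.3.1 says: "The efficacy follow-up period will last until participant's documented disease progression". Protocol 9.1.1 stops treatment at progression. Protocol 9.1.1.3 continues telephone contact for survival every 12 weeks.

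**The concern.** A programmer cannot follow both SAP sections. A death long after the last response assessment is an LFS event under 2.6.1.2 and a censored observation under 2.6.1.3.

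The conflict matters because of how follow-up ends. A participant whose disease progresses without leukemic transformation stops treatment and leaves efficacy follow-up, so no further response assessment is due. Survival calls still record the death. The gap to death grows because assessments were planned to stop, yet the participant would be listed as having an event after two or more missing assessments. The censoring date is then the progression visit, and whether it is applied depends on how long the participant lived afterwards. That is informative censoring of data the trial has already collected.

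**Working it through.** The plan states no LFS median, event count or power, so there is no LFS figure to reproduce.

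**Step 1: D_2.** The formula in SAP 2.6.1.3 is 2 × interval + window. The window is 1 week on treatment and 2 weeks after treatment.

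| Interval in force | D_2 (weeks) |
|---|---|
| Start to C3D1 (8 weeks) | 2×8+1 = 17 |
| C3 to C7 (16 weeks) | 2×16+1 = 33 |
| C7 to C13 (12 weeks) | 2×12+1 = 25 |
| C13 to C25 (24 weeks) | 2×24+1 = 49 |
| After C25 (48 weeks) | 2×48+1 = 97 |
| Efficacy follow-up (about 52 weeks) | 2×52+2 = 106 |

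The SAP does not say which interval applies once assessments have stopped.

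**Step 2: one hypothetical participant.** Non-leukemic progression is found at C7D1 (6 × 4 = week 24). Death follows 30 weeks later without new therapy. Under 2.6.1.2 this is an event at week 24+30 = 54. Under 2.6.1.3 with D_2 = 25 it is censored at week 24. With D_2 = 33 it is again an event at week 54.

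**Step 3: share of post-progression deaths beyond D_2.** Assume exponential survival after progression with median m months. A month is 30.4375/7 = 4.348 weeks (SAP section 4). The share is exp(−ln2 × D_2 / (4.348 m)).

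- m = 6, D_2 = 25: exp(−0.693×25/26.09) = 51%
- m = 6, D_2 = 49: 27%
- m = 3, D_2 = 25: 26%
- m = 3, D_2 = 49: 7%
- m = 12, D_2 = 25: 72%
- m = 12, D_2 = 49: 52%

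The only anchor in the documents is protocol 1.1, which says survival after failure of hypomethylating agents or transformation generally does not exceed 6 months. That is closer to an upper value than a median, hence the range.

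**Step 4: effect on the LFS curve.** This is a Kaplan-Meier simulation in which every rate is an assumption and nobody starts new therapy. Participants alive after progression are censored at their last assessment under both readings, as both SAP sections require. Each pair below gives deaths counted (2.6.1.2), then deaths beyond D_2 censored (2.6.1.3).

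*Slower progression:* monthly hazards 0.045 (non-leukemic progression), 0.015 (leukemia) and 0.010 (death), post-progression median 6 months, D_2 = 25 weeks.

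- 36-month cut-off: LFS at 12 months 60.8% → 59.7%, LFS at 24 months 29.7% → 33.5%, median 15.6 → 15.7 months.
- 18-month cut-off: median 14.6 → 15.8 months.

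*Faster progression:* median times of 8 months (non-leukemic progression), 24 months (leukemia) and 24 months (death), post-progression median 6 months, 36-month cut-off.

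- D_2 = 25 weeks: median 9.3 → 7.9 months.
- D_2 following the SAP schedule: median 9.3 → 8.3 months, LFS at 12 months 39% → 32%.

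*Events lost:* with the slower-progression hazards, a 36-month cut-off and post-progression medians of 3 to 9 months, the share of LFS events lost runs from 11% (3 months, D_2 by schedule) to 33% (9 months, D_2 = 25 weeks).

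The sign varies for a structural reason. The rule keeps post-progression deaths that come before D_2 and moves later ones back to progression as censored. Losing events lifts the curve. Losing known longer survivors from the risk set lowers it.

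**The case against.** The best defence is that 2.6.1.2 is specific to each endpoint and governs, with 2.6.1.3 only supplying the definition of D_2. The LFS sentence in 2.6.1.2 leaves out death where the EFS and PFS sentences include it, which looks deliberate. The opening of 2.6.1.3 also says LFS relies on bone marrow and hematology, while its rule speaks of response assessments. This shows that the harsher reading is not certain. It does not remove the conflict: 2.6.1.3 names LFS in its heading, uses an unqualified term for the event, and nothing in the SAP says which section prevails.

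The second defence is that little depends on it. LFS has no hypothesis test and no comparator. The expansion was not opened, cohort 2 was planned at about 12 participants, and Kaplan-Meier output is conditional on the data. Overall survival counts every death, all deaths are listed, and affected participants would carry a distinct censoring reason. All of this stands and limits the severity. However, 2.6.1.2 still requires each participant's LFS time and event or censoring type to be derived and listed, so the conflict reaches a planned output.

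A reader might go further in three ways that the documents do not support.

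- *That LFS should count all deaths.* Both documents exclude deaths after new antineoplastic therapy.
- *That every death after a non-leukemic progression is censored.* Only those later than D_2, without new therapy, are affected.
- *That LFS is overstated and the regimen favoured.* The slower-progression case raises the 24-month estimate but lowers the 12-month one, and faster progression lowers the median. No single direction is established.

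**Conclusion.** Wrong as written. The SAP contradicts itself on whether LFS deaths fall under the two-missing-assessments rule, and the literal reading of 2.6.1.3 also departs from the protocol. Applied literally, it would discard some recorded deaths after a planned stop in assessments. The loss of about 11 to 33% of LFS events is illustrative. It rests on assumed constant hazards, no new therapy and the chosen D_2; use of new therapy would reduce it. The direction of bias is indeterminate.

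Severity is minor to moderate. No decision rests on LFS, but in a listing of about 12 participants one or two reclassified deaths would be visible.

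**What to change.** In SAP 2.6.1.3, state that for LFS the two-missing-assessments rule applies only to leukemic transformation. State also that every death before new antineoplastic therapy, including death after HSCT, is an LFS event on its date, as 2.6.1.2 and protocol 12.5.1.2 already provide. Since the protocol has no missing-assessment rule for LFS, list the remaining rule for transformation in SAP section 3 as a change.

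The cost is a sentence or two of SAP text and one derivation. No new data are needed, because death dates are already collected.

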Response assessment will be performed by investigator according to the assessment schedule depicted in Table 8-1. Moreover, participants can be assessed for disease response (bone marrow assessment, hematology, transfusion) at any time if clinically indicated as an example if there is a clinical suspicion of progression/relapse, in particular after a participant has achieved a CR.

Bone marrow assessments will be performed at screening and pre-dose on C3D1. From C7D1, bone marrow assessments will be performed every 3 cycles until C13D1 (C7D1, C10D1, C13D1), then every 6 cycles until C25D1 (C19D1 and C25D1) and thereafter every 12 cycles (C37D1, C49D1 etc.) and as clinically indicated during the treatment period.

Hematology assessments will be performed at screening, pre-dose on D1, D8 and D22 of Cycles 1 and 2, and thereafter pre-dose on D1 and D8 of each cycle until end of treatment.

Bone marrow and peripheral blood pathology specimens (i.e. bone marrow aspirate slides, bone marrow biopsy block if applicable, peripheral blood smears) prepared locally for the disease response assessment, should be sent to the Novartis designated central laboratory for storage. This includes specimens taken during the regular work-up of the participant and used as baseline assessment for the study as mentioned in Section 8.2. A copy of the corresponding pathology reports should be collected and sent to the Novartis designated central laboratory for storage. Central morphology review of the pathology specimens may be performed, if deemed necessary. For China only: Storage of the above pathology specimens and reports in a Novartis designated laboratory will be performed, if adequate approval has been obtained from all relevant Chinese authorities.

Participants who discontinue treatment for reasons other than documented disease progression, death, lost to follow-up, or withdrawal of consent, will enter the efficacy follow-up phase.

In the efficacy follow-up phase, hematology assessments must continue to be performed every 3 months, response should be assessed at least every 12 months, and bone marrow assessment should be done at least every 12 months thereafter per Table 8-1, or as clinically indicated any time in case disease progression is suspected. Further information about blood transfusions will be continuously collected throughout the efficacy follow-up period.

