The date of first administration of any study treatment component (sabatolimab or azacitidine or venetoclax) is defined as the first date when a non-zero dose of the respective study drug is administered and recorded on the study treatment eCRF page.

Date of last administration of study treatment (sabatolimab or azacitidine or venetoclax)

The date of last administration of any study treatment component (sabatolimab or azacitidine or venetoclax) is defined as the last date when a non-zero dose of the respective study drug is administered and recorded on the study treatment eCRF page. So both, first and last date of study drug, are derived separately for each drug which is part of the study treatment.

Date of first administration of study treatment (combination)

The date of first administration of study treatment (or start date of study treatment) is defined as the first date when a non-zero dose of any component of the study treatment (sabatolimab, Azacitidine or venetoclax) is administered.

Date of last administration of study treatment (combination)

The date of last administration of study treatment (or start date of study treatment) is defined as the last date when the last non-zero dose of any last component of the study treatment (sabatolimab, Azacitidine or venetoclax) is administered.

Date of last exposure to study treatment component (sabatolimab or azacitidine or venetoclax)

One planned cycle length is 28 days and the start date of a cycle is defined as the first administration of azacitidine within a cycle. Azacitidine is planned to be administered daily every cycle during 7 days at the beginning of each cycle (between Day 1 to Day 9). Sabatolimab is administered every 4 weeks (Q4W), on Day 8 of each cycle, unless there was a toxicity leading to a dosing interval increase. Venetoclax is planned to be administered once a day from day 1 to day 14 of the 28-day cycle.

The date of last exposure to sabatolimab is therefore calculated as:

• Minimum (last date of administration of sabatolimab + 27 days, date of death, last contact date in case participant is lost to follow-up), as sabatolimab injections are given Q4W.

The date of last exposure to azacitidine is calculated as:

• Minimum (last date of administration of azacitidine + 20 days, date of death, last contact date in case participant is lost to follow-up) as the 7 doses of azacitidine are given in the beginning of each cycle.

The date of last exposure to venetoclax is calculated as:

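### The SAP's distance rule for two missing assessments (D2) does not match its own criterion, because response intervals change and the SAP does not say which one applies

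*SAP*

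**What the plan says.** SAP 2.6.1.2 (PFS and EFS) and Protocol 12.5.1.2 censor an event, deaths included, when two or more assessments are missing before it. SAP 2.6.1.3 adds that the missing assessments are consecutive, and that such cases are reported under their own censoring reason. It then replaces the count by a distance: "If the distance is larger than threshold D_2 then the analysis will assume that there are two missing assessments". The threshold is "two times the protocol specified interval between the response assessments plus the allowed window". No value of D2 is given.

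The same section lists several intervals: "From C7D1, bone marrow assessments will be performed every 3 cycles (12 weeks) until C13D1"; then "Every 6 cycles (24 weeks) until C25D1 (C19D1 and C25D1) and thereafter every 12 cycles (48 week"; and "At least every 12 months during follow-up for efficacy". Protocol 8.3.1 gives the same calendar, starting earlier: "Bone marrow assessments will be performed at screening and pre-dose on C3D1". Neither document says which interval enters D2, or what happens where the interval changes.

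**The concern.** Twice the interval plus a window is a sound stand-in for two missed visits when visits are evenly spaced. Here the spacing lengthens as treatment goes on, and the first two gaps differ from each other. A single interval may then be too short, so that an event after one missed visit is censored. It may also be too long, so that an event after two missed visits is kept.

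In the first case a real progression, relapse or death is moved back to the last adequate assessment and labelled as following two missing assessments, which would be untrue. In both cases the choice of interval is left to the programmer, with data from an open-label study already in hand.

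**Working it through.** **Inputs.** SAP section 4 (Appendix, General definitions) states "One planned cycle length is 28 days", so one cycle is 4 weeks. The visits come from Protocol 8.3.1 and SAP 2.6.1.3. The bone marrow window is ±1 week (SAP 2.6.1.3; Protocol section 8). The SAP states no figure for D2, so there is none to reproduce; its conversions of 3, 6 and 12 cycles to 12, 24 and 48 weeks are correct.

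**Calendar.** Week = 4 × (cycle − 1). Baseline 0, C3D1 8, C7D1 24, C10D1 36, C13D1 48, C19D1 72, C25D1 96, C37D1 144, C49D1 192. The gaps are 8, 16, 12, 12, 24, 24, 48 and 48 weeks.

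**Formula.** D2 = 2 × interval + 1 week. An event is censored if its distance from the last adequate assessment exceeds D2.

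**One visit missed (should be kept), nominal dates, weeks:**

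| Last adequate → event | Missed | Distance | D2, interval following last adequate | D2, fixed 12 weeks |
|---|---|---|---|---|
| Baseline → C7D1 | C3D1 | 24 | 2×8+1 = 17, censored | 25, kept |
| C3D1 → C10D1 | C7D1 | 28 | 2×16+1 = 33, kept | 25, censored |
| C7D1 → C13D1 | C10D1 | 24 | 2×12+1 = 25, kept | 25, kept |
| C10D1 → C19D1 | C13D1 | 36 | 2×12+1 = 25, censored | 25, censored |
| C13D1 → C25D1 | C19D1 | 48 | 2×24+1 = 49, kept | 25, censored |
| C19D1 → C37D1 | C25D1 | 72 | 2×24+1 = 49, censored | 25, censored |

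The following-interval reading fails in 3 of 6, or 2 of 5 if baseline does not anchor the distance. A fixed 12 weeks fails in 4 of 6. Widening the window to 2 weeks raises each D2 by 1 and changes none of these results.

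Deaths between visits are caught too. With C10D1 (week 36) as last adequate assessment and D2 = 25, any event after week 36 + 25 = 61 and before C19D1 (week 72) is censored although only C13D1 was missed.

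**Other readings (1-week window):**
- Interval before the last adequate assessment: C3D1 → C10D1 (28 > 17), C10D1 → C19D1 (36 > 25), C13D1 → C25D1 (48 > 25), C19D1 → C37D1 (72 > 49) and C25D1 → C49D1 (96 > 49) are censored after one missed visit.
- Interval ending at the event: C3D1 → C10D1 (28 > 25) is censored after one missed visit. C7D1 → C19D1 (48 ≤ 2×24+1 = 49) and C13D1 → C37D1 (96 ≤ 2×48+1 = 97) are kept after two.
- Fixed 24 weeks (D2 = 49): C19D1 → C37D1 (72) is censored after one missed visit. Baseline → C10D1 (36), C3D1 → C13D1 (40) and C7D1 → C19D1 (48) are kept after two.
- Fixed 48 weeks (D2 = 97): no one-missed event is censored at nominal dates. Those three transitions, C10D1 → C25D1 (60) and C13D1 → C37D1 (96) are all kept after two missed visits.

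**No visit missed.** With a fixed 12 weeks, an on-time progression at C37D1 after C25D1 is censored (48 > 25). If an on-treatment interval of 12 or 24 weeks is carried into follow-up, so is a first assessment 12 months after end of treatment (about 52 weeks, against 25 or 49). With the following interval, or the interval ending at the event, this does not happen on treatment.

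**The case against.** The strongest reply is that SAP 2.6.1.3 lists phase-specific intervals straight after defining D2, so a sensible programmer would use the interval in force and never a fixed 12 weeks. This stands in part. A reader might infer that the rule censors events with no visit missed at all. The documents do not support that in general: it needs a fixed 12 weeks or an on-treatment interval carried into follow-up, or, under some readings, visits at the edges of their windows. But the phase-specific readings still fail where the interval changes.

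A reader might also infer that PFS and EFS are inflated. That is not established either. Some readings drop true events; others keep events that the plan means to censor. For EFS the scope is narrower still. Under SAP 2.6.1.2, participants without CR within the first 6 cycles (C7D1 included) have their event at start of treatment, so only those with CR in that period can be affected later. The baseline → C7D1 case therefore concerns PFS alone. It also assumes that baseline anchors the distance, although SAP 2.5.3.1 calls C3D1 the first efficacy assessment.

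Finally, the practical weight is low. Part 2 was not opened, the endpoints are secondary, Kaplan-Meier output depends on the data (SAP 2.6.1.2), unscheduled assessments count (SAP 2.5.1.2) and shorten real distances, and C37D1 lies 144 weeks after start. All of this stands. It limits the consequence but does not make the rule correct.

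**Conclusion.** The point holds as a defect in a stated rule. D2 is meant to detect two missing assessments, and on the documented calendar no single choice of interval does so. With the following interval, 2 of the 5 one-missed transitions from C3D1 onwards are censored wrongly (3 of 6 if baseline counts, for PFS). With a fixed 12 weeks it is 4 of 6, plus one on-time transition. With a fixed 48 weeks the error runs wholly the other way at nominal dates.

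These results assume 28-day cycles without delay and events dated at nominal visits. The documents do not show how many events would be affected. SAP 1.2 and 2.6.1.2 still have individual times and event or censoring types derived and listed, for a cohort planned at about 12 participants, so one misclassified event would be visible in the listing. The calculation should not be carried over to LFS, where SAP 2.6.1.3 also accepts the more frequent hematology assessments as the anchor.

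**What to change.** Preferably, replace the distance by a count: censor a PFS or EFS event only if two or more consecutive scheduled response visits between the last adequate assessment and the event have no adequate assessment. Use each participant's actual schedule, since Protocol section 8 shifts visits after a delayed cycle.

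If a distance is kept, set D2 to the sum of the next two scheduled gaps after the last adequate assessment, plus 2 weeks:
- baseline, if it is an anchor: 8+16+2 = 26
- C3D1: 16+12+2 = 30
- C7D1: 12+12+2 = 26
- C10D1: 12+24+2 = 38
- C13D1: 24+24+2 = 50
- C19D1: 24+48+2 = 74
- C25D1 and later on treatment: 48+48+2 = 98

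Two weeks are needed because both visits can move. C7D1 a week early and C13D1 a week late are 24+2 = 26 weeks apart, which a 1-week allowance (25) would still censor. At nominal dates these thresholds censor every event at the third scheduled visit (for example C10D1 → C25D1, 60 > 38).

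Either way, state whether baseline can anchor the distance, and give the rule for the step from end of treatment to the 12-month follow-up assessments. The cost is one SAP paragraph and a short look-up or count in the program, with no new data.
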